2.3 Primary Endpoint(s)

Safety:

1. Incidence and severity of AEs and Adverse Events of interest (urinary retention, withdrawal symptoms) over the course of the study. AEs are recorded at visits 2,3,4,5,6 and 7.
2. Adverse Events of special psychiatry interest (nervousness, anxiety, panic attacks, insomnia, aggression, mania, suicidal ideation, development/worsening of depression) over the course of the study
3. Suicidal Adverse Events and Adverse Events suggestive of abuse potential will be analysed, and detailed narratives provided
4. Lab parameters: Haematology and chemistry recorded at visit 1,2,6 and 7. Urinalysis recorded at visit 1 and 2.
5. Absolute change from end of the Screening Placebo Run-In Period in ECG readings and Week 8 (Visit 6). ECG parameters of interest include: ventricular rate, QT interval, corrected QT interval, PR interval, and QRS duration
6. Absolute change from end of the Screening Placebo Run-In Period to each visit in standardised cuff systolic and diastolic blood pressure and radial heart rate

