3.1 Sample Size

Approximately 95 subjects are expected to be enrolled into the 2-week, single-blind (subject blind) Screening Placebo Run-In Period. It is expected that 20% of subjects will not qualify for randomization after Screening Placebo Run-In.

The study is expected to randomize approximately 78 subjects into the double-blind treatment where subjects will be allocated to litoxetine (dose titration over 10 mg, 20 mg, 30mg) or matched placebo BID in a 2:1 ratio. A post randomisation dropout rate of 30% has been estimated, resulting in 60 evaluable subjects.

A sample size of 60 subjects is expected to provide a 95% confidence interval for a rate of safety events of 50% with a width +/- 14%. The sample size calculation is based on the precision of the estimate of the primary outcome, safety events, using a rate of 50% which would provide the most conservative sample size.

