4.1 Study Populations

The study population will consist of subjects with UI. Subjects must be able to provide written consent and meet all the inclusion criteria and none of the exclusion criteria.

A valid efficacy measurement is defined as a valid number of incontinence episodes as recorded in the bladder diary and uploaded in the eCRF at Visit 2 and Visit 6, i.e. either as 0 or greater than 0.

There are 4 analysis populations for this study:

Randomised population:

Defined as all subjects randomised to treatment (Visit 2).

Safety population:

Defined as all subjects who are randomised to treatment (Visit 2), receive study drug, and undergo at least 1 visit.

Intent-to-Treat (ITT) population:

Defined as all subjects who are randomized to treatment (Visit 2), receive at least one dose of study drug and have a valid efficacy measurement at Baseline (Visit 2).

Per Protocol (PP) population:

Defined as those subjects who are randomised, receive at least one dose of study drug, provide a valid efficacy measurement at Baseline (Visit 2) and a valid end of study primary efficacy endpoint (Visit 6), and have completed the study without a major protocol deviation.

The following populations are defined for analysis purposes:

1. Enrolled Population: each subject that signed the Informed Consent form and entered the Screening Period.
2. Completers Population: each subject that completed the trial, per protocol.
3. Full Analysis Set Population: each subject which is in either ITT or PP population.

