5.3 Safety variables

All safety variables will be derived from the eCRF.

Adverse Event (AE) An AE is defined as any untoward medical occurrence in a patient or clinical investigation subject administered a pharmaceutical product and which does not necessarily have a causal relationship with this treatment.

Non-Treatment-Emergent Adverse Event (non-TEAE)

When an AE occurs after written consent has been obtained but before the first dose of treatment study drug (Visit 2 date), the AE will be considered a non-treatment emergent AE. Adverse Events, related to abnormal laboratory parameters, that were identified at Visit 2, when blood samples were collected before the first dose of the study drug, are considered non- TEAEs.

Treatment-Emergent Adverse Event (TEAE)

An AE that occurs from the time the subject receives his first dose of treatment study drug (Visit 2 date) until his last study visit (Follow-up Visit date) will be considered a treatment-emergent AE (TEAE) regardless of the assessed relationship to the administration of the study drug.

Immediately Reportable Adverse Event (IRAE)

Immediately reportable AEs (IRAEs) are AEs that must be reported to the Sponsor within 24 hours of the study site being informed of the IRAE.

Immediately reportable AEs include:

- All SAEs
- Overdose
- Pregnancy
- AEs that result in a subject's withdrawal from the study

For litoxetine in the current study and with the current posology, an overdose should be considered as any dose above 60 mg taken per day.

Serious Adverse Event (SAE)

A serious adverse event (SAE) is any untoward medical occurrence or effect that at any dose:

- Results in death
- Is life threatening
- Requires hospitalisation or prolongation of existing hospitalisation
- Results in persistent or significant disability or incapacity
- Is a congenital anomaly or birth defect
- Is another medically important condition

An important medical event that is not immediately life-threatening or will result in death or hospitalisation, but which may jeopardize the subject or may require medical intervention to prevent 1 of the outcomes listed above, should be reported as "serious" as well.

Adverse Event of Special Interest (AESI)

Adverse events of special interest are:

1. Adverse Events of Interest include urinary retention and withdrawal symptoms.

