6.3 General Methodology

Safety

Safety data will be presented and analysed using the Safety Population.

The primary safety analyses include all treatment emergent adverse events defined as any AE started after Visit 2. The analysis will be carried out with point estimates and Clopper Pearson 95% confidence intervals.

Descriptive statistics will be provided for all variables in the summary tables by treatment group according to the type of variable summarised.

Quantitative variables will be summarised by using n (number of subjects per group), arithmetic mean, standard deviation (SD), median and range (minimum and maximum).

Categorical variables will be summarised by using frequency distributions and percentages.

The number of Adverse Events and the number and the percentage of patients experiencing those events, will be summarised by treatment group. Differences between groups will be evaluated using Chi-square test or Fisher's exact test. Subgroup analysis of differences between groups of AEs will be performed separately for patients who had an adverse event while on the 10mg dose (AE started from Visit 2 and Visit 3), 20 mg dose (AE started from Visit 3 and Visit 4) and 30 mg dose (AE started from Visit 4 and Visit 6). Subjects with adverse events who deviated from the protocol dosage will be highlighted in the footnotes.

Shift tables will be used to describe the evaluation of clinical significance for laboratory values, 12-Lead ECG and physical examination.

For all analyses, hypothesis testing will be carried out at the alpha = 0.05 level (two-sided) when comparing treatments. P-values will be rounded to three decimal places. Statistical significance will be declared if the rounded p-value will be less than or equal to 0.05.

Efficacy

For the PP efficacy analysis of incontinence episodes, only valid efficacy endpoints at Visit 6 will be used. For the ITT efficacy analysis of incontinence episodes, valid and imputed endpoints at Visit 6 will be used. The imputation method is described in section 6.1. No LOCF from baseline will be used for any efficacy analysis.

Descriptive statistics will be provided for all variables in the summary tables by treatment group according to the type of variable summarised.

Quantitative variables will be summarised by using n (number of subjects per group), arithmetic mean, standard deviation (SD), median and range (minimum and maximum).

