6.7 Safety Analysis

The general objectives of this study are to establish the safety, tolerability and efficacy of litoxetine in men and women who suffer from UI. The primary analyses will focus on safety, describing the adverse events with point estimates and Clopper Pearson 95% confidence intervals. All safety analyses will be conducted on the safety population.

All AEs will be coded using the MedDRA dictionary (version 20.1).

1. Incidence and severity of Treatment Emergent Adverse Events and Treatment Emergent Adverse Events of interest (urinary retention, withdrawal symptoms) over the course of the study.

The Treatment Emergent Adverse Events (TEAEs) and the TEAEs of Interest will be summarised by treatment group. The SOCs and PTs will be used for tabulation. The number of TEAEs/TEAEs of interest and the number and the percentage of patients with at least one AE will be presented by SOC and PT for each treatment group. Within each SOC and PT, the highest severity grade attained will be reported, for AEs with divergent severities.

TEAEs/TEAEs of interest will be described with point estimates and Clopper Pearson 95% confidence intervals.

The analysis of treatment emergent adverse events is the primary safety endpoint, the analysis of TEAEs of interest is considered as part of the secondary safety analysis.

2. Treatment Emergent Adverse Events of special psychiatry interest (nervousness, anxiety, panic attacks, insomnia, aggression, mania, suicidal ideation, development/worsening of depression) over the course of the study

The Treatment Emergent Adverse Events of special psychiatry interest will be summarised by treatment group. The SOCs and PTs will be used for tabulation. The number of AEs and the number and the percentage of patients with at least one AE will be presented by SOC and PT for each treatment group. Within each SOC and PT, the highest severity grade attained will be reported, for AEs with divergent severities.

Adverse events will be described with point estimates and Clopper Pearson 95% confidence intervals.

3. Treatment Emergent Suicidal Adverse Events and Adverse Events suggestive of abuse potential

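### The primary TEAE rate is a crude proportion that counts event-free early leavers as non-events, so each arm's risk over the study is understated or at best unbiased; a supplementary time-to-event estimate would show by how much.

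*SAP*

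**What the plan says.** Safety is the primary objective. The first primary endpoint in SAP 2.3 is "Incidence and severity of AEs and Adverse Events of interest (urinary retention, withdrawal symptoms) over the course of the study".

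- **Estimator.** SAP 6.3, on treatment-emergent events: "The analysis will be carried out with point estimates and Clopper Pearson 95% confidence intervals". SAP 6.7 repeats this and says "the percentage of patients with at least one AE will be presented by SOC and PT for each treatment group". The outcome is thus ever/never per subject.
- **Denominator.** SAP 6.7: "All safety analyses will be conducted on the safety population". SAP 4.1 gives that population as "Defined as all subjects who are randomised to treatment (Visit 2), receive study drug, and undergo at least 1 visit".
- **Window.** SAP 5.3 counts an event from the first randomised dose "until his last study visit (Follow-up Visit date) will be considered a treatment-emergent AE (TEAE"). For a completer this is 13 weeks after randomisation. For an early leaver it ends at whatever visit was last.
- **Dropout.** SAP 3.1: "A post randomisation dropout rate of 30% has been estimated, resulting in 60 evaluable subjects".
- **Missing safety data.** SAP 6.1 imputes partial medication dates and no other safety value.
- **Between-arm comparison.** The chi-square or Fisher tests (SAP 6.3, 6.8) and the exact logistic model (SAP 6.8) use the same ever/never outcome, with no exposure term.

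Neither document plans a person-time rate, a Kaplan-Meier curve or a cumulative-incidence estimate.

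**The concern.** An ever/never proportion estimates risk over a stated period only if everyone is observed for that period or has the event first. Here the endpoint refers to the whole study and a sizeable dropout is expected, yet someone last seen in week 1 without an event carries the same weight as someone seen event-free to week 13. Events after such a subject's last contact are not counted, but the subject still is.

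Two features of the trial make this relevant. The top dose level starts two weeks after randomisation, so a week-1 leaver counts as event-free for dose levels never taken. Withdrawal symptoms are a named event of interest, and Protocol 4.3 says they usually appear within days of stopping. A subject who stops and does not come back is scored as free of them.

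The exact binomial interval covers sampling error only. It does not reflect this shortfall, or any distortion of the arm comparison if event-free departures differ between arms.

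**Working it through.** **1. The plan's own figures.** Of 78 subjects randomised 2:1, 52 go to litoxetine and 26 to placebo. The Clopper-Pearson half-width at an observed 50% is:

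| n | Half-width |
|---|---|
| 52 (all litoxetine) | 14.2 points |
| 60 | 13.2 points |
| 40 (two thirds of 60) | 16.2 points |

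The stated ±14% fits 52 best, that is, with leavers kept in the denominator. The dropout figures do not agree with each other: 78 × 0.70 = 54.6, not 60, and 60 of 78 means 18/78 = 23.1% lost.

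**2. Inputs for the size of the effect.**
- From the documents: 50% event rate (SAP 3.1); 30% dropout; 8 weeks of treatment, (70 − 14)/7; 13 weeks from randomisation to Visit 7, (105 − 14)/7; taper plus follow-up of 1 + 4 = 5 weeks.
- Assumed: leaving is unrelated to adverse events and uniform over weeks 0 to 8. The time to first event is Weibull with a risk of 50% at the target time T, with shape 1 (constant hazard) or 0.5 (front-loaded). Leavers are observed for 0 further weeks (no return) or 5 (return).

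**3. Formula.** With dropout d, shape k and extra observation e:

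F(s) = 1 − 0.5^((s/T)^k)

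m = mean of F(min(t + e, T)) for t uniform on 0 to 8

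crude rate = (1 − d) × 0.50 + d × m

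Hand check for T = 13, k = 1, e = 0: m = 1 − [13/(8 × 0.693)] × (1 − 0.5^(8/13)) = 1 − 2.344 × 0.347 = 0.186. The crude rate is 0.35 + 0.30 × 0.186 = 0.406.

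**4. Results at d = 0.30 (true risk 50%).**

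| Target | Shape | Return? | m | Crude rate |
|---|---|---|---|---|
| 13 weeks | 1 | no | 0.186 | 40.6% |
| 13 weeks | 1 | yes | 0.376 | 46.3% |
| 13 weeks | 0.5 | no | 0.298 | 43.9% |
| 13 weeks | 0.5 | yes | 0.434 | 48.0% |
| 8 weeks | 1 | no | 0.279 | 43.4% |
| 8 weeks | 1 | yes | 0.473 | 49.2% |
| 8 weeks | 0.5 | no | 0.361 | 45.8% |
| 8 weeks | 0.5 | yes | 0.486 | 49.6% |

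The 8-week rows count events up to Week 8 only. In the return rows, part of a leaver's observed time is after stopping drug. Among 52 litoxetine subjects, 26 expected cases become 21.1 to 25.0 (13 weeks) or 22.5 to 25.8 (8 weeks).

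**5. Less dropout.** With d = 18/78 the 13-week range is 42.8% to 48.5%. If half of the 30% leave after an adverse event and so already count as events, d is 0.15 and the range is 45.3% to 49.0%.

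**6. Limits.** If every leaver already had an event, there is no shortfall. If all 30% left at once, event-free, and stayed in the denominator unobserved, the rate would be 0.70 × 50% = 35%.

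**7. Between arms.** With equal true risk, dropouts of 40% and 10% give a spurious difference of (0.40 − 0.10) × (0.50 − m). That is 2.0 to 9.4 points over 13 weeks and 0.4 to 6.6 points over 8 weeks. These two dropout rates are illustrative; the documents give none by arm.

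**The case against.** The strongest reply is that leavers are not simply lost. An early-terminating subject is to have the Visit 6 procedures, which include an adverse-event query, and is asked to taper and return for Visit 7 (Protocol 4.3, 7.1.6; schedule footnote 4). With full return, the shortfall against 8-week risk is under 1 point, and against 13-week risk it is 2.0 to 3.7 points. This largely stands, although return is requested and not assured.

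It can also be said that the estimator matches the SAP's definition of a TEAE, that crude proportions are usual in a trial this small, and that the planned interval is about ±14 points. The SAP also reports time to onset, treatment duration, reasons for discontinuation and events by dose period. A reader could therefore see unequal exposure, but none of these corrects the proportion.

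Three stronger readings are tempting, and the documents do not support them.

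- **That 30% of subjects are lost event-free.** The plan calls this a loss of evaluable subjects, not of adverse-event follow-up. Subjects who stop for intolerance count as events if an adverse event was recorded. The 30% itself conflicts with 60 of 78. The denominator also requires at least one visit, so it is not everyone dosed.
- **That the sample-size text treats leavers as not evaluable for safety while the analysis counts them.** SAP 3.1 does tie ±14% to 60 subjects, but Protocol 8.10 and SAP 1.6 tie it to the treatment arm, and the figure fits all 52. The mismatch is a separate matter to reconcile.
- **That the arm comparison will be biased in a known direction.** Nothing in the documents suggests which arm would lose more event-free subjects.

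**Conclusion.** The concern holds in limited form. The primary TEAE proportion ignores differing follow-up. Each arm's risk over the course of the study is understated or, at best, unbiased, because events after last contact can only be missed.

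The size cannot be settled from the documents. For a true 50% risk and 30% non-AE dropout, the shortfall is 2.0 to 9.4 points over 13 weeks or 0.4 to 6.6 points over 8 weeks. The low ends need full return of leavers and front-loaded events. The high ends need no return and a constant hazard. The ranges rest on uniform dropout and a Weibull event time. Lower dropout, or leavers who already had an event, would shrink them. Unequal event-free dropout could move the between-arm comparison either way.

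A reader might infer that the primary analysis should be replaced. The documents do not require that: Protocol 8.1 names the proportion with Clopper-Pearson interval as the primary analysis, and it is a valid description of what was observed. This is a cheap improvement, not a defect that invalidates the safety analysis.

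**What to change.** Keep the crude proportion with Clopper-Pearson interval as the primary analysis. Add to SAP 6.3 and 6.7, before unblinding, a supplementary analysis by randomised arm: a Kaplan-Meier estimate of time to first TEAE, censored at last contact, read at Week 8 and at the end of follow-up, with 95% confidence intervals. Define last contact explicitly, so that early-termination and Visit 7 attendance by leavers is used.

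An exposure-adjusted rate is optional. If given, split it by dose period (10 mg, 20 mg, 30 mg, taper, off-drug), because one pooled rate assumes a constant hazard across the titration.

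The cost is SAP wording, one table and one figure, from onset and visit dates already collected. There are two drawbacks. The estimate assumes that leaving for reasons other than an adverse event is unrelated to later adverse-event risk, and its intervals will be slightly wider than the crude ones.

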3.2 Discussion of Study Design

Litoxetine's initial development as an antidepressant (discontinued in the 1990's due to absence of effect) has included 12 phase 1 studies in HVs. The current development in Urinary

Incontinence (UI) is based on the scientific rationale and preclinical data showing effect on both detrusor and sphincter, and the definition of the condition used in this protocol adheres to clinical practice and ICS guidelines. The present study, for which safety is the primary endpoint, will include patients diagnosed with UI and is designed as a phase 1/2a study. The inclusion of a placebo arm is based on recent European Medicines Agency (EMA) guidelines for the development of medications for UI ([European Medicines Agency, UI Guideline 2013](#)). The dose titration posology serves to explore safety and tolerability following a sequential increase in dose, rather than as a fixed dose regimen. The selection of safety parameters for determination of subject eligibility and for safety analysis reflect the FDA's recommendation for evaluation of SSRIs, including attention to psychiatric adverse events and events indicative of abuse potential. Inclusion of subjects in the age range 18-70 is reflective of the expectation that UI may affect all age groups, with increasing prevalence with age (FDA Guidance General Consideration for the Clinical Evaluation of Drugs). The choice of efficacy endpoint (percentage change from end of the Placebo Run-in Period to Week 8 in the number of incontinence episodes/24 hours) is a clinical measure to explore whether litoxetine has a clinically relevant treatment effect on patients' reported symptomatology and patient reported outcome measures in a clinical practice setting. The 2-week Screening Placebo Run-In Period serves to control for the placebo effect which is anticipated to be relatively large.

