7.1.2 Eligibility Assessment Visit – Visit 2 (Day 14)

The following procedures are to be completed during the Eligibility Assessment Visit at time points outlined on the Schedule of Assessments ([Appendix 2](#)).

- Record current medications
- Measure and record vital signs (blood pressure, heart rate, and body temperature)
- Complete full physical examination
- Complete the C-SSRS, BDI-II, BAI, PSQI
- Determine subject's PVR
- Collect urine for pregnancy test in women of childbearing potential
- Collect urine for dipstick test (If test is positive for nitrates and leukocyte esterase, take history of signs and symptoms of urinary tract infection and perform urine culture. If urine culture and clinical signs and symptoms are positive, the subject cannot be enrolled in the study, but can be re-screened at a later date, as long as s/he does not meet exclusion criterion 11 [chronic, or recurrent (> 4 per year) urinary tract infections]. Microscopic evaluations will be performed if the dipstick test is positive. If the dipstick test is positive and the microscopic evaluation is abnormal these results will be recorded as an AE with the follow-up of the AE reported to the Medical Monitor.)
- Draw blood for haematology and biochemistry tests
- Perform 12-lead ECG
- Review bladder diary
- Verify eligibility (inclusion/exclusion criteria)
- Randomise subject
- Collect single-blind study drug for Run-in Period and perform drug accountability
- Dispense double-blind study drug
- Query for AEs

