1.6 Study Summary

This is a Phase 1/2a, double-blind, randomised, placebo-controlled, parallel-group study in subjects, male and female, 18 to 70 years old diagnosed with UI.

The study will include a 2-week, single-blind (subject blind) Screening Placebo Run-In Period and an 8-week double-blind Treatment Period. The treatment period is a dose titration posology starting with 10 mg BID for 1 week, escalated to 20 mg BID for 1 week, and subsequently escalated to 30 mg BID for 6 weeks for a total treatment duration of 8 weeks. The Treatment Period will be followed by a 1 week Dose-tapering Period and subjects will return to the clinic for a safety Follow up Visit 4 weeks after treatment is completed. This provides a total study duration of 15 weeks.

Safety assessments will be conducted throughout the trial and will include physical examinations, vital signs, evaluation of psychiatric status (suicidality, depression symptoms, anxiety and sleep related symptoms), clinical laboratory evaluations, 12-lead electrocardiograms (ECGs), and adverse events (AEs).

Efficacy will be assessed by number of urinary incontinence episodes and the number of incontinence pads used at the end of the Placebo Run In period and after 8 weeks of double blind study treatment.

Approximately 95 subjects are expected to be enrolled into a 2 week, single-blind (subject blind), Screening Placebo Run-In Period. It is expected that 20% of subjects will not qualify for randomization after Screening Placebo Run-In.

The study is expected to randomize approximately 78 subjects into the double-blind treatment where subjects will be allocated to litoxetine (dose titration 10 mg, 20 mg, 30 mg) or matched placebo BID in a 2:1 ratio. A post randomisation dropout rate of 30% has been estimated, resulting in 60 evaluable subjects. This sample size is expected to provide confidence intervals for the most conservative rate of safety events (50%) that are +/- 14% for the widest observed intervals in the treatment arm.

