6.4 Patient Disposition

Disposition of patients will be presented by treatment group and overall for all patients.

The number of patients included in each of the randomised, safety, ITT, and PP populations will be summarised for each treatment group and overall.

Randomised patients who discontinued from the study prematurely will also be presented with a breakdown of the reasons for discontinuation by treatment group and overall for the randomised population.

Major and minor protocol violations will be presented in the listings only.

The number of patients who need a dose reduction will be presented with means of descriptive statistics. Frequencies and percentages will be used to describe the number of subjects who took a given amount of study drug (10/20/30 mg) at each visit.

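### The adverse event tables by dose level assign events by visit window, not by dose taken, and the windows last 1, 1 and 6 weeks, so figures compared across dose levels confound dose with time at risk

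*SAP*

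**What the plan says.** SAP 6.3 (Safety) plans this: "Subgroup analysis of differences between groups of AEs will be performed separately for patients who had an adverse event while on the 10mg dose", with that dose defined as onset between Visit 2 and Visit 3. The other two levels are defined in the same way: "20 mg dose (AE started from Visit 3 and Visit 4" and "30 mg dose (AE started from Visit 4 and Visit 6". Treatment groups are compared by Chi-square or Fisher's exact test.

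For dosing that departs from the schedule, the provision is: "Subjects with adverse events who deviated from the protocol dosage will be highlighted in the footnotes". Protocol 3.1 and SAP 3 allow a subject who cannot tolerate 30 mg BID to go back to 20 mg BID and stay in the study.

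The planned schedule is "10 mg BID for 1 week, escalated to 20 mg BID for 1 week, and subsequently escalated to 30 mg BID for 6 weeks" (SAP 1.6). SAP 6.4 will tabulate the number of subjects "who took a given amount of study drug (10/20/30 mg) at each visit", and SAP 6.8 will describe the TEAEs that led to a dose reduction. Protocol 3.2 states the purpose of the design: "The dose titration posology serves to explore safety and tolerability following a sequential increase in dose".

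**The concern.** The label refers to the dose the subject was on, while the rule refers to calendar time. The two part company in three places.

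- **Dose reductions.** Once a subject has gone back to 20 mg BID, any event that starts before Visit 6 is still counted under 30 mg. The footnote flags subjects but moves no events. A reduction that the protocol permits is arguably not a deviation from the protocol dosage, so it may not be flagged at all.
- **Boundary days.** Doses are escalated at Visits 3 and 4. No rule says which window takes an event that starts on those days.
- **Time at risk.** The third window is six times as long as each of the other two, and the SAP gives neither exposure time nor a rate.

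Because the titration is there to study tolerability as the dose rises, a reader is likely to look along the row from 10 to 30 mg. That reading would mix any effect of dose with the length of observation.

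**Working it through.** **Inputs from the documents.** Visit days are 14, 21, 28 and 70 for Visits 2, 3, 4 and 6 (Protocol 7.1, for example "Eligibility Assessment Visit – Visit 2 (Day 14"). The visit tolerance is ±2 days. About 78 subjects are randomised 2:1, so 52 litoxetine and 26 placebo. Tests are two-sided at 0.05 on the rounded p-value. The assumed dropout is 30%.

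**Assumptions.** The documents give no adverse event rates. The weekly risk h of an event, the weekly decline factor r and the risks by arm below are illustrative.

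**1. Window lengths.** 21 − 14 = 7 days, 28 − 21 = 7 days and 70 − 28 = 42 days. This reproduces the planned 1, 1 and 6 weeks (8 in total), a ratio of 42/7 = 6. With the tolerance, the short windows can run 3 to 11 days and the long one 38 to 46.

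**2. Boundary days.** If both end days are included, the windows hold 8 + 8 + 43 = 59 days over 57 calendar days, so the Visit 3 and Visit 4 days count twice. Half-open windows hold 7 + 7 + 42 = 56 days with none shared.

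**3. Crude percentages across dose levels, no dose effect, constant risk.** The percentage with an event is h in a 1-week window and 1 − (1 − h)^6 in the 6-week window.

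| h per week | 10 mg window | 30 mg window | Ratio |
|---|---|---|---|
| 2% | 2.0% | 11.4% | 5.7 |
| 5% | 5.0% | 26.5% | 5.3 |
| 10% | 10.0% | 46.9% | 4.7 |
| 20% | 20.0% | 73.8% | 3.7 |
| 40% | 40.0% | 95.3% | 2.4 |

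Event counts differ by 6. If 30% leave at a constant rate over the 8 weeks and the denominator stays at everyone randomised, the ratio of percentages is 4.7 at h = 2% and 2.5 at h = 30%.

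**4. Risk that falls after the start.** If weekly risk is multiplied by r each week, the 30 mg to 10 mg ratio of event counts is r² + r³ + … + r⁷. This gives 3.8 at r = 0.9, 2.4 at r = 0.8, 1.4 at r = 0.7, 0.86 at r = 0.6 and 0.49 at r = 0.5.

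**5. The planned test within each window (52 versus 26, Fisher, exact enumeration).**
- Equal risk, 10% per week in both arms: the risk ratio is 1.0 in both window lengths. The false-positive rate is 3.0% in a 1-week window and 3.3% in the 6-week window.
- A constant drug effect, 10% versus 5% per week: in a 1-week window the risk difference is 5 points, the risk ratio 2.0 and the power 4%. In the 6-week window (46.9% versus 26.5%) they are 20 points, 1.8 and 37%.

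An effect that does not change with dose is thus far more likely to reach significance in the 30 mg window.

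**6. Denominator.** SAP 6.3 gives none specific to these windows. If it were the whole safety population and dropout differed by arm, the within-window contrast would shift. Suppose 10 of 52 litoxetine and 1 of 26 placebo subjects leave before Visit 4, and true risk afterwards is 40% in both arms. The table would then show 42 × 0.4 / 52 = 32% against 25 × 0.4 / 26 = 38%.

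**The case against.** The strongest reply is that no 30 mg versus 10 mg comparison is planned. The SAP compares litoxetine with placebo, and matched placebo follows the same visits, so each litoxetine window has a placebo window of equal length. Step 5 confirms that window length creates no spurious drug effect. This part of the objection stands, provided dropout is similar in the arms or the denominators are updated. It does not cover the pattern of significance across windows, which depends on window length even when the drug effect is constant.

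Three stronger readings are tempting but not supported:
- A reader might infer that 30 mg must look several times worse. That needs crude figures read across doses and a roughly constant risk. Step 4 shows that the direction can reverse.
- A reader might infer that the primary safety conclusion is at risk. The primary analysis is of all TEAEs by treatment group with Clopper-Pearson intervals (SAP 6.3 and 6.7) and does not use these windows.
- A reader might infer that the SAP counts boundary days twice, or keeps early leavers in later denominators. It states neither; it is silent or ambiguous on both.

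Two further points are fair. An event that prompts a reduction started on 30 mg and is correctly placed, so only events starting after the reduction are mislabelled. The documents do not say how many reductions are expected. Also, sorting litoxetine subjects by dose taken groups them by tolerance after randomisation, whereas visit windows keep the randomised comparison.

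**Conclusion.** The point holds as a defect of a secondary safety display. The stated rule puts events under a dose that the subject may no longer have been taking, leaves two boundary days unassigned, and sets a 6-week window beside two 1-week windows with no exposure adjustment. Crude figures across dose levels can therefore differ 2.4- to 5.7-fold in patient percentages with no dose effect, if weekly risk is constant at 2% to 40%. With strongly front-loaded events the count ratio can drop below 1. For a constant drug effect of 10% versus 5% per week, power moves from 4% to 37% with window length alone. The size of the mislabelling after dose reductions cannot be estimated from the documents. The point is worth correcting because the design is meant to describe tolerability as the dose rises, but it does not threaten the primary analysis.

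**What to change.** In SAP 6.3:
- Keep the visit-window comparison with placebo as the randomised contrast, and label the columns as titration periods.
- Make the windows half-open, for example from Visit 3 up to but not including Visit 4. Say how the window is closed for a subject who leaves before that visit, since early termination is recorded as Visit 6.
- Use subjects still on treatment at the start of each window as its denominator.
- Show subject-weeks at risk and events per subject-week by arm and window beside each count, and note that crude columns are not comparable across doses.
- Add a supportive litoxetine display by dose at onset, using the recorded dose reductions.

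Under constant risk, the rate per subject-week brings the 30 mg to 10 mg ratio to 1.0. It does not separate dose from time since starting: at r = 0.8 the rate ratio would be 2.36/6 = 0.39. Rates should therefore be read against concurrent placebo.

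The cost is SAP wording and modest programming. The dose-at-onset display is non-randomised and descriptive. There is no clinic visit between Visit 5 (Day 35) and Visit 6 (Day 70), so dose-change dates in that interval must come from whatever dosing and adverse event action records exist.
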